## 9. ADVERSE EVENT REPORTING REQUIREMENTS

### 9.1 Adverse Event Characteristics

- **CTCAE term (AE description) and grade:** The descriptions and grading scales found in the revised NCI Common Terminology Criteria for Adverse Events (CTCAE) version 4.0 will be utilized for AE reporting. All appropriate treatment areas should have access to a copy of the CTCAE version 4.0. A copy of the CTCAE version 4.0 can be downloaded from the CTEP web site:

[http://ctep.cancer.gov/protocolDevelopment/electronic\\_applications/ctc.htm](http://ctep.cancer.gov/protocolDevelopment/electronic_applications/ctc.htm).

- **For expedited reporting purposes only:**
  - AEs for the agent(s) that are listed above should be reported only if the adverse event varies in nature, intensity or frequency from the expected toxicity information which is provided.
  - Other AEs for the protocol that do not require expedited reporting are outlined in the next section (Expedited Adverse Event Reporting) under the sub-heading of Protocol-Specific Expedited Adverse Event Reporting Exclusions.
- **Attribution** of the AE:
  - Definite – The AE is *clearly related* to the study treatment.
  - Probable – The AE is *likely related* to the study treatment.
  - Possible – The AE *may be related* to the study treatment.
  - Unlikely – The AE is *doubtfully related* to the study treatment.
  - Unrelated – The AE is *clearly NOT related* to the study treatment.

### 9.2 Expedited Adverse Event Reporting

9.2.1 Investigators **must** report to the Overall PI any serious adverse event (SAE) that occurs after the initial dose of study treatment, during treatment, or within 30 days of the last dose of treatment on the local institutional SAE form.

9.2.2 DF/HCC Expedited Reporting Guidelines

Investigative sites within DF/HCC will report AEs directly to the DFCI Office for Human Research Studies (OHRs) per the DFCI IRB reporting policy.

### **9.2.3 Protocol-Specific Expedited Adverse Event Reporting Exclusions**

For this protocol only, the AEs/grades determined to be related to chemotherapy treatment or the disease under study (i.e. breast cancer) and not the study intervention (ear acupuncture) do not require expedited reporting to the Overall PI or the DFCI IRB. However, they still must be reported through the routine reporting mechanism (i.e. case report form).

### **9.3 Expedited Reporting to Hospital Risk Management**

Participating investigators will report to their local Risk Management office any participant safety reports or sentinel events that require reporting according to institutional policy.

### **9.4 Routine Adverse Event Reporting**

All Adverse Events **must** be reported in routine study data submissions to the Overall PI on the toxicity case report forms. **AEs reported through expedited processes (e.g., reported to the IRB) must also be reported in routine study data submissions.**

## **10. STATISTICAL CONSIDERATIONS**

### **10.1 Accrual**

In this feasibility pilot study, the target sample size is 26 patients enrolled during a 3-month period.

### **10.2 Endpoints**

Enrolled patients will receive an educational reading material during the first cycle of chemotherapy and ear acupuncture during cycles 2 and 3. The primary feasibility endpoint consists of three parts. The intervention will be deemed feasible if: (a) at least 20 patients (80%) are enrolled by September 2017; (b) all 20 patients complete at least 75% of the acupuncture sessions; and (c) all 20 patients complete at least 9 out of 12 (75%) assessments. Secondary endpoints will investigate changes in patient-reported outcomes relative to baseline (T1) for the following time points: after the intervention (T2), Day 2, and Day 5 after chemotherapy infusion (T3 and T4). Changes will be compared between cycle 1 (no acupuncture) and cycles 2 and 3 (acupuncture).

For the secondary endpoints, we are primarily interested in the effect of acupuncture therapy compared with no acupuncture; therefore, comparisons will be based on the

averages of the assessment change scores over a time interval during acupuncture (cycles 2 and 3) compared with the change during the same time interval of cycle 1.

For example, if  $T_{ij}$  is the score at time  $i$  ( $i = 1$  to 4) during cycle  $j$  ( $j = 1$  to 3), then three pairwise differences will be of interest:

PD1: Change between  $T_2$  and baseline:  $[(T_{22} - T_{12}) + (T_{23} - T_{13})]/2$  vs.  $(T_{21} - T_{11})$

PD2: Change between  $T_3$  and baseline:  $[(T_{32} - T_{12}) + (T_{33} - T_{13})]/2$  vs.  $(T_{31} - T_{11})$

PD3: Change between  $T_4$  and baseline:  $[(T_{42} - T_{12}) + (T_{43} - T_{13})]/2$  vs.  $(T_{41} - T_{11})$

### **10.3 Sample Size**

Sample size considerations for the secondary endpoints are based on a one-sample t-tests, 80% power, and an overall type-I error of 0.1 (two-sided), which will be divided equally between the three pairwise comparisons (0.033 for each). The detectable effect size based on these operating characteristics is 0.625.

For our main secondary endpoint of ESAS Total Score, it has been reported that the minimal clinically important difference (MCID) for improvement, based on within-patient change, is 5.7 points ( $SD=11.6$ ,  $N=105$ ). For the purposes of this protocol, a clinically significant improvement in ESAS Total Score will be defined as a 6-point decrease.

If the within-patient correlation of change scores between  $T_2$  and baseline is 0.6, then the estimated standard deviation of the pairwise difference (PD1, above) would be 9.4.

There would be 80% power to detect a difference in change scores of 5.9 points. The table following summarizes detectable differences in ESAS Total Score for varying within-patient correlations.

Detectable Differences in ESAS Total Score based on one-sample t-tests, two-sided alpha = 0.033, and 80% power

Within-patient Correlation	Estimated Standard Deviation	Detectable Difference
0.6	9.4	5.9
0.7	8.3	5.2
0.8	7.0	4.4
0.85	6.3	3.9
0.9	5.5	3.4

Therefore, for a sample of 26 patients, we would have at least 80% power to detect the ESAS Total Score MCID, for within-patient correlations of at least 0.6.

## **10.4 Data Analysis**

Baseline demographic, disease characteristics, prior treatment, and comorbidities will be compared using the relevant descriptive methods for continuous and categorical variables.

For the primary, feasibility endpoint, the proportion of patients who satisfy the definition of feasibility will be summarized with a 90%, exact binomial confidence interval. For samples of size 20 and 26, the confidence interval will be no wider than 0.4 and 0.35, respectively.

Pairwise differences (PD1-PD3, above) of the ESAS Total Score will be analyzed using one-sample t-tests and a comparison-wide error rate of 0.1, which will be divided equally among the three pairwise comparisons. Model-based approaches will also be used to investigate changes over time. We will also present the proportion of patients who had at least a 6-point decrease on ESAS Total Score from T1 at each time point with exact confidence intervals. Comparable analyses will be conducted for ESAS Physical Score, ESAS Emotional Score, the individual symptom scores, State Anxiety Scale scores, and MET nausea scores at each time point between cycle 1 and cycles 2 and 3.

Patient-reported outcomes will also be presented graphically over time by chemotherapy cycle. Safety data will be reported for all patients according to CTCAE Version 4.0.

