## **7. SPECIMEN/DATA COLLECTION PROCEDURES**

The pre-infusion assessments will be collected before patients are given educational materials (cycle 1) or receive acupuncture (cycles 2 and 3) on Day 1 of cycles 1-3. The post-intervention assessments will be repeated after the completion of reading educational material or acupuncture on Day 1, Day 2 and Day 5 of cycles 1-3.

Study measures will be collected according to the following schedule (Table 1):

Table 1. Schedule of Study Measures

	Tracking Log	Consent Form	Educational Booklet	ESAS	STAI	MAT	Medication Log	Event Log	AES	Acupuncture Tx Form
Recruitment	X	X					X			
Cycle 1				X	X	X				
Pre-Intervention	Day 1			X						X
Post-Intervention	Day 1			X		X				
	Day 2			X		X				
	Day 5			X		X			X	
Cycle 2				X		X				
Pre-Intervention	Day 1			X		X				X
Post-Intervention	Day 1			X		X				
	Day 2			X		X				
	Day 5			X		X			X	
Cycle 3				X		X				
Pre-Intervention	Day 1			X		X				X
Post-Intervention	Day 1			X		X				
	Day 2			X		X				
	Day 5			X		X			X	

Study measures will be collected by the study CRC (cycle 1) and/or by the study acupuncturists (cycle 2 and 3). The post-acupuncture assessments will be collected by the study acupuncturists. Assessments will be coordinated with ear acupuncture visits when possible, so that patient convenience is maximized. Day 2 and Day 5 assessments will be filled out by the patients at home and returned to the study CRC at the next visit. The home assessments will be put in an envelope to keep the confidentiality. To facilitate completion, patients will be reminded by phone and by email to complete the home assessments. Patients may also choose to complete the home assessments over the phone with the study coordinator.

The following measures will be collected:

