### **8.1 Ear Acupuncture Protocol**

At the infusion during the 1st cycle, the study patients will receive an educational booklet developed by National Cancer Institute. This booklet includes facts about chemotherapy and its side effects. It highlights ways that a patient can care for herself before, during, and after treatment. No acupuncture will be performed during the first infusion cycle. The patient will be encouraged to read the booklet during the infusion. During the second and third infusion cycles, the study patients will receive a 30-minute session of a standardized ear acupuncture treatment.

At each visit, the study patient will be sitting in an infusion chair either reading the booklet (cycle 1) or receiving ear acupuncture treatment (cycles 2 and 3). For each ear acupuncture session, the patient will have ear acupuncture therapy administered to each ear. After the skin of the ear is cleaned with alcohol, six acupuncture needles (SEIRIN®, No. 1., 30 mm x 0.16 mm) will be inserted into acupuncture points bilaterally. The depth of needle insertions is around 2-3 millimeters. Then, acupuncture needles will be gently manipulated to increase stimulation. The patient will be asked to orally report the needling intensity level on a scale from 0-10 (0 being feeling nothing at all and 10 being the strongest one can imagine). Then, the needles will remain in the sites for 30 minutes while receiving IV infusion. After 30 minutes, another round of gentle manual manipulation will be performed prior to the removal of the needles. Figure 3 and Table 2 presents the names and locations of ear acupuncture points.

If a study patient misses an acupuncture treatment, the patient will be asked to make up the missed treatment session during the next chemotherapy infusion, so that a total of 2 consecutive sessions of acupuncture will be provided. The total number of acupuncture sessions received will be recorded for each participant. Any side effects related to the acupuncture will be collected by treating acupuncturists.

An outline of the acupuncture protocol and a summary of acupuncture points to be used are presented below in Figure 3 and Table 2, respectively.

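### PD1-PD3 each need six ESAS Total scores but are tested by one-sample t-tests with no rule for a missing score; specifying the model already planned, and testing PD1-PD3 in it, would lose less power.

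*Combined protocol and SAP*

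**What the plan says.** Section 10.2 defines PD1, PD2 and PD3 as the mean change from T1 to T2, T3 or T4 over cycles 2 and 3, set against the same change in cycle 1. Section 10.4 gives the test: "Pairwise differences (PD1-PD3, above) of the ESAS Total Score will be analyzed using one-sample t-tests and a comparison-wide error rate of 0.1", with the 0.1 split equally in three. Its next sentence adds supplementary model-based work on change over time, without naming a model, a covariance, a contrast or a missing-data assumption.

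On size, Section 10.1 says "the target sample size is 26 patients enrolled during a 3-month period". Section 10.3 says "The detectable effect size based on these operating characteristics is 0.625" and concludes: "Therefore, for a sample of 26 patients, we would have at least 80% power to detect the ESAS Total Score MCID", for correlations of 0.6 or more. Section 10.2 counts enrolment as feasible if "at least 20 patients (80%) are enrolled by September 2017". Section 10.4 gives confidence interval widths for the feasibility proportion at both 20 and 26 patients, but no section gives power at 20.

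On collection, Section 7 says "Day 2 and Day 5 assessments will be filled out by the patients at home". It also provides phone and email reminders and the option of completing the forms by phone. Day 1 measures are collected by study staff.

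**The concern.** A PD cannot be computed unless all six of its scores are present. With no rule for gaps, the natural reading is that a patient missing any one of the six leaves that t-test, and the scores the patient did give are discarded. The plan itself allows for gaps: 9 of 12 assessments meets its feasibility rule. The power statement covers 26 patients only and makes no visible allowance for loss.

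What is at stake is the precision of the preliminary efficacy estimates (Objective 2), which are meant to inform a later randomized trial. An unwritten rule could also be settled after the data are seen.

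**Working it through.** **Inputs.** From Section 10.3: SD of a within-patient change 11.6; clinically significant change 6 points (published value 5.7); overall two-sided alpha 0.1, so 0.1/3 = 0.033 per PD; 80% power. From Section 10.1: n = 26. The documents give no missing-data rate; the rates below are assumptions.

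**Reproducing the plan.**
- The SD column follows from SD(PD) = 11.6 × √(1.5 − √2 × ρ). At ρ = 0.6 this is 11.6 × √0.6515 = 9.36, shown as 9.4. The other rows give 8.28, 7.04, 6.33 and 5.53, as tabulated.
- By the noncentral t distribution, the effect size detectable with 80% power is 0.624 at n = 25 and 0.610 at n = 26. The stated 0.625 therefore matches 25 patients. Any allowance for loss is at most one patient, and it is not explained.

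**Power for 6 points by number of complete patients** (one-sample t-test, alpha 0.1/3):

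| Correlation (SD) | n = 26 | n = 24 | n = 20 | Smallest n for 80% |
|---|---|---|---|---|
| 0.6 (9.4) | 84% | 80% | 71% | 24 |
| 0.7 (8.3) | 92% | 89% | 82% | 20 |
| 0.8 (7.0) | 98% | 97% | 93% | 15 |
| 0.85 (6.3) | 99% | 99% | 97% | 13 |
| 0.9 (5.5) | >99% | >99% | 99% | 10 |

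For the published 5.7 points at SD 9.4, power at n = 26 is about 79%.

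**The 0.6 row is conservative.** The plan's formula treats the cycle 2 and cycle 3 changes as uncorrelated when it averages them. With a common correlation of 0.6 among all three cycles, SD = 11.6 × √(1.5 × 0.4) = 8.99. Power is then 87% at 26, 82% at 23 and 75% at 20.

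**How gaps remove patients.** A given PD uses 6 of the 12 assessments, so a patient missing one assessment at random has a 6/12 = 50% chance of leaving that PD. If each home form is missing independently with probability 10%:
- PD1 uses Day 1 forms only and keeps all 26 patients.
- PD2 and PD3 each need three home forms. Complete patients: 26 × 0.9³ = 19.0.
- If the change from the one available acupuncture cycle is used when the other is missing: 26 × 0.9 × (1 − 0.1²) = 23.2 patients.

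**Simulated power for 6 points** (26 enrolled, PD SD 9.4, correlation 0.6, values missing at random):

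| Situation | Complete-case t-test | t-test using the available acupuncture cycle | Mixed model on cycle changes | Mixed model on all scores |
|---|---|---|---|---|
| No gaps | 84% | 84% | 85% | 86% |
| 10% of home forms missing (PD2, PD3) | 67-70% | 76% | 78% | 82% |
| Four patients without cycle 3 | 75-76% | 81-82% | 84% | 83% |
| Four patients leaving after cycle 1 | 75-76% | 75-76% | 80% | 78% |

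Ranges come from separate simulations. The all-scores model used REML with Kenward-Roger degrees of freedom, assumed patient and patient-by-cycle variances of 100 and 40, and 804 to 1,587 runs per situation. The change-score model used 3,000 runs and the t-test rule 20,000. Rejection under the null, against a nominal 0.033, was 0.028-0.044 for the all-scores model, 0.030-0.042 for the change-score model and 0.030-0.038 for the t-test rule.

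**Holm at family-wise 0.1** (thresholds 0.033, 0.05, 0.1; n = 26, SD 9.4, assumed correlation 0.5 between PDs). Power per PD rises from 0.84 to 0.91 if all three PDs have a 6-point effect and to 0.87 if two do, and is essentially unchanged if one does. Family-wise error was at most 0.09.

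**The case against.** - *The plan already has a model.* A reader might infer that modelling is absent. It is not: Section 10.4 announces it directly after the t-tests. What stands is that the model is unspecified, supplementary and not the test of PD1-PD3.
- *Heavy loss is unlikely.* A reader might infer that power would roughly halve, because 10% loss on every form leaves 26 × 0.9⁶ = 13.8 complete patients and about 50% power. The documents do not support that scenario. Staff collect the Day 1 forms, and home forms are backed by reminders and phone completion. Loss of home forms is the realistic case.
- *The t-test can be kept.* Complete-case analysis is not stated, and a one-sentence rule recovers much of the loss. This stands. The model gains a further 2 to 6 points of power over that rule for lost home forms.
- *Only one row is exposed, and 20 is a feasibility threshold rather than the planned sample.* Both are true. But 0.6 is the plan's own lower bound and worked example, and power at 20 is easily stated.
- *The all-scores model is ambitious.* It has 20 covariance parameters and was simulated only at n = 26. This also stands, and it is why the simpler change-score model is offered.

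**Conclusion.** The point holds as an analysis choice worth improving. PD1-PD3 have no missing-score rule, and if complete cases are used, the 80% power at correlation 0.6 survives the loss of only about two patients. Under an assumed 10% loss of home forms, PD2 and PD3 fall to about 67-70%; a mixed model holds about 78-82%, and a simple t-test rule about 76%. PD1 is untouched in that case.

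A reader might infer that the trial is underpowered or that its feasibility result is in doubt. Neither follows. With 26 complete patients, power for the plan's 6-point difference is 84% even in its least favourable row; four of five rows keep at least 82% at 20 patients; and these are secondary endpoints.

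The power gains rest on assumed missing rates, on scores missing at random and, for the all-scores model, on one assumed set of variances.

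**What to change.** 1. Specify the model already planned and make it the main test of PD1-PD3: a linear mixed model on all available T1-T4 scores from cycles 1-3, with cycle-by-time fixed effects, a pre-specified covariance, PD1-PD3 as contrasts and Kenward-Roger degrees of freedom. A simpler version models the up to three cycle change scores per patient, with cycle fixed effects and a random patient intercept. Keep the t-tests as a sensitivity analysis. As a minimum alternative, keep the t-test and state that the available acupuncture cycle is used when the other is missing.
2. State power at 20 as well as 26 patients across the plan's correlation range.
3. Separately, replace the equal alpha split with Holm at the same family-wise 0.1. It never rejects less; its small downside is that matching confidence intervals are less simple.

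The cost is wording and slightly more analysis, with no extra patients or visits. The model relies on missing at random, so it does not remove bias if patients skip forms because they feel worse. It helps little when patients leave after cycle 1: with the covariance known, it recovers 24% of the lost information at correlation 0.6 and 6% at 0.9.

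### The equal Bonferroni split of the 0.1 error rate over PD1-PD3 is valid, but Holm's step-down would hold the same 0.1 and never reject fewer contrasts (optional efficiency gain on a secondary endpoint)

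*Combined protocol and SAP*

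**What the plan says.** Section 10.2 defines PD1, PD2 and PD3. Each compares the average change from T1 over cycles 2 and 3 (acupuncture) with the change over the same interval in cycle 1 (booklet), at the post-session, Day 2 and Day 5 assessments respectively: "then three pairwise differences will be of interest".

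Section 10.3 sets "an overall type-I error of 0.1 (two-sided), which will be divided equally between the three pairwise comparisons", which it gives as 0.033 each. The test and target are stated there too: "Sample size considerations for the secondary endpoints are based on a one-sample t-tests, 80% power". It adds: "The detectable effect size based on these operating characteristics is 0.625".

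Section 10.4 repeats the rule for the analysis of ESAS Total Score: one-sample t-tests at "a comparison-wide error rate of 0.1, which will be divided equally among the three pairwise comparisons". Neither section mentions a step-down or any other sequential procedure.

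ESAS Total Score is the main secondary endpoint. The primary endpoint is feasibility, in three parts (10.2), and lies outside this family of tests.

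**The concern.** Under an equal split, each contrast is judged at 0.033 whatever the other two show. If one contrast is clearly rejected, its share of the error allowance is not passed on to the remaining ones. With 26 patients and power planned at about 80% per contrast, that unused allowance could decide whether a second or third time point is declared different. The abstract says that the data are meant to inform a later randomized trial, so it matters which of the three time points respond.

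What is at stake is the efficiency of the secondary tests. The validity of the plan is not in question.

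**Working it through.** **Inputs from the plan.** n = 26 (10.3); one-sample t-test with target power 80% (10.3); overall two-sided error 0.1 over three contrasts (10.3, 10.4); detectable standardised effect 0.625 (10.3).

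**Input not in the plan.** The correlation between the PD contrasts. It is assumed, over the range 0.3 to 0.7.

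**Step 1: the plan's own figures.**
- 0.1/3 = 0.0333, stated as 0.033. The three shares add to 0.1, so familywise error is at most 0.1.
- Power of one contrast comes from the noncentral t with 25 degrees of freedom and noncentrality d√n. With d = 0.625, 0.625 × √26 = 3.19, and power at 0.0333 is 81.9%. The stated 80% is reproduced within 2 points.
- The effect with exactly 80% power at n = 26 and level 0.033 is 0.611. That value is used below, so that Bonferroni starts at 80%. (0.625 fits n = 25, where power is 80.2%.)

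**Step 2: what Holm guarantees.** Order the p-values. Test the smallest at 0.1/3 = 0.0333, the next at 0.1/2 = 0.05 and the last at 0.1, stopping at the first failure.
- *Error.* Suppose m of the three nulls are true. The first true null to be rejected must have p at or below 0.1/m. By the union bound the chance of that is at most m × 0.1/m = 0.1, with no condition on dependence.
- *Never fewer rejections.* Every Holm threshold is at least 0.0333, so any contrast that Bonferroni rejects, Holm rejects too.
- *No change in the chance of any rejection.* The smallest p-value is still tested at 0.0333.

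**Step 3: size of the gain.** Simulation with n = 26, three one-sample t-tests, 100,000 trials per scenario and correlations 0.3, 0.5 and 0.7. Power is per real contrast; ranges run over the correlations.

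| True standardised effects | Bonferroni | Holm |
|---|---|---|
| 0.611, 0.611, 0.611 | 80% | 87-89% |
| the same, all three rejected | 57-66% | 78-82% |
| the same, at least one rejected | 93-97% | 93-97% (identical at each correlation) |
| 0.611, 0.611, 0 | 80% | 83-84% |
| 0.611, 0, 0 | 80% | about 0.2-0.3 point higher |

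No Bonferroni rejection was lost in any trial.

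**Step 4: realised familywise error.**

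| True nulls | Bonferroni | Holm |
|---|---|---|
| three | 7.6-9.4% | identical |
| two (other effect 0.611) | 5.8-6.3% | 7.5-8.7% |
| one (other effects 0.611) | about 3% | about 8% |

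With one true null, Bonferroni spends only about 0.033 of the 0.1 that the plan allows. Holm spends more of it and stays inside the limit.

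**The case against.** The strongest reply is that nothing here is wrong. Bonferroni is valid and pre-specified, it agrees between 10.3 and 10.4, and the detectable-difference table uses the same level. The tests are secondary in a single-arm feasibility pilot, and no decision rule depends on how many contrasts are rejected. All of that stands, and it is why the change is optional.

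Four stronger readings are tempting, and the documents do not support them.

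- *Holm gives more power on every contrast.* The gain depends on another contrast also being rejected, and it is negligible when only one effect is real. Nothing in the documents says that all three effects are of full size. Treatment is one 30-minute session on Day 1 of the cycle (8.1), the earlier service reported relief immediately after treatment (2.2), and PD3 looks at Day 5.
- *Several real effects are likely because the contrasts share patients and T1 scores.* Sharing correlates the estimates; it does not make the true effects nonzero. Higher correlation also shrinks Holm's per-contrast gain, from 89% at 0.3 to 87% at 0.7.
- *The change is free.* It needs no extra patients and stays within 0.1, but realised error under partial nulls rises. A contrast that is significant under Holm may also have a Bonferroni-level (96.7%) interval that includes zero. The plan specifies no intervals for PD1 to PD3, so this matters only if they are reported.
- *The power statement in 10.3 is undermined.* It is not: 0.033 is the first Holm step, so the figures hold under either method.

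**Conclusion.** The equal split is a sound choice that can be improved. For the same overall two-sided 0.1, Holm rejects everything Bonferroni rejects and sometimes more. These guarantees need no assumption about the correlation between contrasts.

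The size of the gain does rest on assumptions: n = 26 with complete data, normally distributed differences, and correlations of 0.3 to 0.7, which the plan does not give. It is 7 to 9 points per contrast if all three effects equal 0.611, 3 to 4 points if two do, and practically nothing if one does. The chance of finding at least one effect is the same under both methods.

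This is an optional efficiency gain for a secondary endpoint. The feasibility conclusion is untouched.

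**What to change.** Before outcome data are seen:

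- In 10.4, replace the equal division with: *controlled at an overall two-sided 0.1 by the Holm step-down procedure across PD1-PD3*. This would also align 10.4, which calls the rate comparison-wide, with 10.3, which calls it overall.
- In 10.3, add that 0.033 is the first Holm step, so the stated detectable differences stand as a minimum-power statement. The table needs no recalculation.
- If intervals for PD1 to PD3 are shown, label them as Bonferroni-level and note that they may include zero for a contrast that is significant under Holm.

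The cost is one sentence and one clause, plus the note if intervals are reported. No patients or assessments are added. The sponsor accepts a higher realised familywise error under partial nulls, within the 0.1 already granted.

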### **7.3 The MASCC Antiemesis Tool (MAT)**

The MASCC Antiemesis Tool (MAT) is a validated questionnaire developed by the Multinational Association of Supportive Care in Cancer (MASCC). MAT assesses the domains of nausea and vomiting through the acute and delayed phases of CINV. Each phase is assessed by four items that measure the occurrence of CINV, duration of nausea (10-point scale), and frequency of vomiting (number of episodes). MAT will be collected on Day 2 and Day 5 during each cycle of chemotherapy.

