##### *Information about this brief form:*

The MASCC Antiemesis Tool (MAT) is a way to help your doctors and nurses be sure you get the best care there is to prevent nausea and vomiting from chemotherapy. By filling out this form, you can help us make sure that you are having the best control of these possible side effects.

Here are the definitions used on this form:

[figure not shown]
**Vomiting:** The bringing up of stomach contents.

**Nausea:** The feeling that you might vomit.

Please answer all questions. There are no right or wrong answers, only your impression.  
If you have any concerns about how or when to complete this form, please ask!

Please notice that Question #4 and Question #8 have a different style. These questions are **scales**.  
For this type of question, just circle the number from 0 to 10 that most closely resembles your experience with your nausea and vomiting and write the number in the box to the right. An example of this form of question (but dealing with parking) is given below. Feel free to practice with this example or ask one of us to go over it with you.

How much difficulty did you have parking your car today?

(Write the number in this box)

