## MASCC Antiemesis Tool

[figure not shown]
Please fill this out **the day after chemotherapy** on:

		
Day	Month	Day of the Week

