## MASCC Antiemesis Tool

This page asks about the period from the day after to 4 days after chemotherapy.  
So it asks about the time after the first 24 hours.

Please fill this out four days after chemotherapy on:

				
	Day	Month	Day of the Week	
Delayed Nausea and Vomiting				
5) Did you vomit 24 hours or more after chemotherapy?	 Yes	 No		(Select one)
6) If you vomited during this period, how many times did it happen?				(Write the number of times in this box)
7) Did you have any nausea 24 hours or more after chemotherapy?	 Yes	 No		(Select one)
8) If you had nausea, please circle or enter the number that most closely resembles your experience. How much nausea did you have over this time period?				(Write the number in this box)
				

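### Does the analysis of MAT nausea scores fail because MAT has no pre-infusion (T1) score?

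*Combined protocol and SAP*

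**What the plan says.** **Endpoint rule (10.2).** "Secondary endpoints will investigate changes in patient-reported outcomes relative to baseline (T1) for the following time points": after the intervention (T2), Day 2 (T3) and Day 5 (T4). The contrasts PD1, PD2 and PD3 set the average change in cycles 2 and 3 against the change in cycle 1. They are introduced as an example, and no instrument is exempted.

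**Analysis text (10.4).** PD1 to PD3 are assigned to ESAS Total Score. Comparable analyses are then promised for the other ESAS scores, State Anxiety, "and MET nausea scores at each time point between cycle 1 and cycles 2 and 3". No instrument called MET is defined anywhere in the document. MAT is the dedicated nausea and vomiting tool.

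**When MAT is collected (7.3 and Appendix III).** "MAT will be collected on Day 2 and Day 5 during each cycle of chemotherapy". The acute page is to be filled out "the day after chemotherapy". The delayed page reads "Please fill this out four days after chemotherapy on" a date to be entered. The form's instructions identify the two rating scales: "Please notice that Question #4 and Question #8 have a different style". By contrast, 7.1 and 7.2 collect ESAS and STAI four times per cycle.

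**Error rate.** Section 10.3 sets an overall two-sided 0.1 for the secondary endpoints, "which will be divided equally between the three pairwise comparisons (0.033 for each"). Section 10.4 gives "a comparison-wide error rate of 0.1, which will be divided equally among the three pairwise comparisons", in a sentence about ESAS Total Score.

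**The concern.** Read literally, 10.2 requires a T1 value for every secondary patient-reported outcome, and MAT cannot supply one. Objective 2 names chemotherapy-induced nausea and vomiting, and MAT is the instrument devoted to it. If the written contrasts were the only ones allowed, this outcome would have no analysis. Otherwise the analyst has to drop the T1 term and choose an error rate for two comparisons where the plan counted three, possibly with the data in hand. In a single-arm study meant to inform a later randomised trial, an undefined contrast on a named symptom would be an avoidable source of discretion.

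**Working it through.** **Inputs.** N = 26 (10.1); 80% power, overall two-sided type I error 0.1 split over three comparisons, detectable effect 0.625 (10.3); contrasts PD1 to PD3 (10.2); MAT days (7.3, Appendix III). Table 1 is broken in the available text and is not used.

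**1. The plan's own figure.** For a one-sample t-test with standardised effect d, power = P(T' > t(1 − α/2; n − 1)), where T' is noncentral t with n − 1 degrees of freedom and noncentrality d√n.
- d = 0.625, n = 26, α = 0.1/3 = 0.0333: power 81.9%.
- Solving for 80% power: d = 0.610 at n = 26 and α = 0.0333; d = 0.6247 at n = 25 and α = 0.033.

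The printed 0.625 is reproduced to within one patient.

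**2. Which contrasts MAT supports.** Write T_ij for the score at time i in cycle j. With chemotherapy on Day 1, the day after is Day 2 (i = 3) and four days after is Day 5 (i = 4). MAT exists only for i = 3 and i = 4.
- PD1 needs T1 and T2: neither exists.
- PD2 and PD3 need T1: it does not exist.

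So 0 of 3 can be formed.

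**3. What remains when T1 is dropped.** Rearranging PD2:

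PD2 = [(T32 − T12) + (T33 − T13)]/2 − (T31 − T11) = D3 − B,

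where D3 = (T32 + T33)/2 − T31 and B = (T12 + T13)/2 − T11.

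PD3 = D4 − B in the same way, with D4 = (T42 + T43)/2 − T41.

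B is the between-cycle difference in the pre-infusion score. MAT asks only about time after chemotherapy, so B has no counterpart on this scale. D3 and D4 are what is left: the Day 2 and Day 5 scores, acupuncture cycles against cycle 1. That matches the closing words of 10.4. The scores are item 4 (acute page) and item 8 (delayed page).

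**4. Error rate for two tests (n = 26, 80% power).**

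| Level per test | Sum over two tests | Detectable d |
|---|---|---|
| 0.0333 (carried over) | 0.067 | 0.610 |
| 0.05 (0.1 divided by two) | 0.10 | 0.572 |
| 0.10 (no split) | 0.20 | 0.501 |

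Moving from the first row to the second lowers the detectable effect by 1 − 0.5717/0.6104 = 6.3%. Both rows keep within 0.1. Only the third row exceeds it, and reaching it means ignoring the split that 10.3 and 10.4 describe. The documents give no MAT standard deviation, so none of this can be put in MAT points.

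**The case for a change.** The best case for a change is this. Section 10.2 states the change-from-T1 rule without qualification, and the example that follows only supplies notation. The closing words of 10.4 cover the whole list, including ESAS sub-scores and State Anxiety, for which comparable plainly means PD1 to PD3; nothing marks MAT as different. No MAT formula, number of tests or error rate is written, and the three levels in the table above give different detectable effects. A few sentences would settle it at no cost.

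The factual part stands: PD1 to PD3 cannot be formed for MAT, and the MAT contrast is nowhere written as a formula. The inference from it is weaker.

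- A comparable analysis need not be an identical one. Section 10.4 names the time points and the cycles, and MAT has just two time points. The same section also provides for model-based approaches to change over time, which do not need a T1 score.
- The missing error rate is not peculiar to MAT. ESAS Physical, ESAS Emotional, the individual symptoms and State Anxiety have no specific rule either. Dividing 0.1 by two within MAT would leave multiplicity across all these scales where it is, so the choice is a preference.
- The 6-point responder definition belongs to ESAS Total Score. It does not carry over as it stands to any 0 to 10 item, MAT included.

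**Conclusion.** No change is needed. This is missing detail that analysts fill sensibly, together with a clerical slip (MET for MAT). Anyone holding the data would find no T1 score on the MAT forms and would compare Day 2 and Day 5 between cycle 1 and the mean of cycles 2 and 3. No printed figure is wrong and no planned conclusion is altered.

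The effect is small. Keeping 0.033 for each of two tests is merely conservative, and the alternative split changes the detectable effect by about 6%. MAT has no part in the feasibility endpoint or the ESAS power table. The ESAS nausea item, collected four times per cycle, still supports all three written contrasts for nausea.

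The conclusion assumes that MET means MAT, that a patient who reports no nausea is scored 0 on item 4 or 8 (sensible on a 0 to 10 scale, but not stated in 7.3 or Appendix III), and that the T1 responder analysis is not applied to MAT. Reporting the two MAT contrasts descriptively with confidence intervals would suit a single-arm feasibility study and is compatible with the present text.
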